Dondzila et al. found that older adults who considered themselves physically active actually walk more than those who do not rate themselves as physically active.¹⁴ The Physical Activity Guidelines for Americans recommend 150 minutes each week of moderate intensity aerobic activity or 75 minutes each week of vigorous intensity aerobic activity.¹⁵ The Centers for Disease Control and Prevention (CDC) reported that “1 out of 5 adults (21%) meet the 2008 Physical Activity Guidelines”.¹⁶ For the older adults, the threshold amount of physical activity associated with better physical health is >8000 steps/day and/or >20min/day at an intensity of >3 Metabolic Equivalent (METS) and for better mental health, >4000 steps/day and/or >5min/day at >3METS.¹⁷ Men aged 65-69 years performed the highest steps per day (>9,126 steps/day) and women aged 85+years were in the lowest category of steps per day (<276 steps/day).¹⁸

Currently, 10,000 steps per day is a widely promoted dosage-based walking program. In older adults, increased lower and upper body strength, endurance, lower body flexibility, and agility/balance were significantly and positively associated with walking 6500 or more steps per day.¹⁹ Low-activity, non-depressed older adults were able to maintain and/or improve their mental health.²⁰ High volume of steps led to an increase in the Timed Up and Go (TUG) score, 30-second leg lifts and 2-minute walking distance.²¹

Because of the detrimental effects of sedentary lifestyle, interventions to increase physical activity are a public health priority.²² There are many instruments available to track the amount of physical activity of an individual subjectively and objectively.²³ A self-report physical activity questionnaire is a cost-effective method to obtain physical activity data. The International Physical Activity Questionnaire (IPAQ) is the most commonly used physical activity questionnaire worldwide. It has two versions, a 31-item long form and the nine-item short form. The short form records the amount of time spent in sitting, walking, moderate- and vigorous-intensity activities in the last 7 days.²⁴

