There are four purposes to this study. The primary purpose of this study is to evaluate the impact of walking as an exercise component of VR on both primary and secondary vestibular-specific outcome measures. The primary outcomes are mCTSIB, TUG test, DGI, and DHI, while the secondary outcomes are the total number of visits and length of interventions (in weeks). The second purpose is to evaluate whether pedometers increase the adherence of older adults with vestibular issues to a walking program. This will be measured by change in physical activity, as represented by International Physical Activity Questionnaire (IPAQ) Walking Metabolic Equivalent of Task (MET)-minutes/week and IPAQ Total Physical Activity MET-minutes/week scores from the IPAQ short form during the episode of care (admission and discharge) and on four-weeks follow-up compared to those patients who only received instructions to walk without a pedometer. The third purpose of this study is to establish test-retest reliability of the TUG test on older adults with dizziness. Lastly, the fourth purpose of this study to investigate if the TUG, DGI, and mCTSIB are significant and strong predictors of the DHI in older adults with dizziness. Protocol #1365169 “Predictors of Disability in the Older Adults” is being performed to supplement the number of subjects for the fourth objective of this study.

Study Design

Research Design

1. Experimental Design. To answer the first and second study objectives, a pragmatic, randomized, prospective, clinical study on 54 older adults with dizziness will be utilized. This will be conducted at Florida Hospital Sports Medicine and Rehabilitation locations that offer vestibular therapy. These are in East Orlando and Winter Park.
2. Correlation Design. A correlation analysis will be performed on the data collected on 54 subjects in the experimental design to establish the test-retest reliability of the Timed Up and Go.
3. Cross-sectional Descriptive Design. A regression analysis will be performed on three predictors of the Dizziness Handicap Inventory, obtained from the data collected on 54 subjects in the experimental design and from Florida Hospital Sports Medicine and Rehabilitation Physical Therapy medical charts from June 2015 to June 2018 that met the inclusion and exclusion criteria that were outlined in the Protocol #1365169.

Study Agent, Device, and/or Intervention Description

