The VRWP group will have VR with an instruction to increase their number of steps daily to at least 3,000 steps using the pedometer (VR plus walking plus pedometer group). They will receive pedometers (Fitbit Zip), instructions on how to use the pedometer, step log forms, with home instruction handout to walk more at least more than ten minutes at a time. This group will be instructed to wear a pedometer on or below the waist such as belt, waistband, or in trousers' pocket, during waking hours, all day, except for bathing or swimming. A clip designed to keep the Fitbit Zip clipped to the clothing will be provided. There is no charging time. Fitbit Zip uses a replaceable watch battery that can last up to 6 months. The participants will record on their activity log the number of steps shown on the step display at the end of the day. The Fitbit Zip will be device inclusive. Subjects will not be given instruction to program their information or synchronize their Fitbit Zip with an application software on a smart phone, tablet, or any computer device. The daily step log form will be given to the research staff every visit for recording. The research staff will encourage their participants to increase their daily steps at least 10% until they achieve at least 3,000 steps daily. The older adults in the group will be trained on how to use the pedometers before they take them home, and will have the opportunity to review this instruction with the research staff on consecutive visits if needed. There may be cost associated with the study in case of lost or malfunction from using the pedometer due to the subject will be encouraged but not required to replace the pedometer. The subject will continue to be the VRWP group and this situation will be reported in the discussion of results.

The VRW group will receive VR and a time-based instruction to walk more daily at least 10 minutes at a time (VR plus walking no pedometer group). This group will be instructed on the benefits of walking (similar to the first group) but will not be given the pedometer. They will have home instruction handouts to walk more at least more than ten minutes at a time and a walking log sheet. The research staff will instruct their participants to increase their daily time at least 10% until they achieve at least 30 minutes of walking exercise daily. The walking log sheet form will be given to the research staff by the participant every visit for recording.

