The VR (control) group will follow the conventional VR physical therapy without the encouragement of walking and without specification of walking in the home exercise program.

The use of an assistive device can be recommended for any subject in any group by the research staff to maximize safety. The patient may need to purchase the assistive device.

Participants who do not belong to the intervention group with pedometer will receive a pedometer after they completed the study. They will receive instructions on how to use the pedometer prior or on the day of their last visit.

Study Visits

For the experimental design that will be conducted at Florida Hospital locations, the following data will be collected as standard of care by the physical therapist during initial evaluation, and if more time is needed, during the first follow-up physical therapy appointment: mCTSIB, TUG, DGI, DHI, age, gender, body mass index, home situation, Functional Comorbidity Index (FCI) total, ability to drive, medications and insurance type. After the subject signs the informed consent, the study coordinator will be notified by the research staff to conduct a retrospective chart review on the physical therapy initial evaluation and first follow-up visit, if applicable, of the subject. The study coordinator will extract the following baseline measurements from the subject's medical record: DGI, mCTSIB, DHI, TUG and socio-demographic data that include age, gender, body mass index, home situation (lives alone or with social support), Functional Comorbidity Index (FCI) total, ability to drive (able or unable), medications for vertigo and insurance type (Medicare/Non-medicare). Based on the retrospective chart review, the study coordinator will determine if the subject is eligible to participate in the study.

Visit 1: Once the study coordinator determined that the subject is eligible to participate in the study, the subject will be assigned a research number and will be randomized into one of the three intervention groups. The research staff can initiate or continue the VR program. For the test-retest reliability of the TUG test, there will be one practice trial followed by two final performances that will be included in the data analysis. The subject will also be asked to complete the IPAQ-short form questionnaire. The test-retest reliability of TUG and the IPAQ-short form questionnaire are for research purposes only.

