Visit 2: The research staff can initiate the research intervention according to the intervention group.

Visit 3 to visit prior to discharge: The research staff can continue the VR and intervention according to the intervention group.

Discharge or last visit: All outcome measures (DGI, TUG, mCTSIB, DHI and IPAQ) will be reassessed. Discharge scores for DGI, TUG, mCTSIB and DHI are standard of care, while IPAQ is for research purposes only. The total number of visits and length of

interventions (in weeks) for every participant will be recorded as secondary outcome measures. These research data will be forwarded to the study coordinator, and will be stored in a locked cabinet and password protected Florida Hospital computer.

Four-weeks after discharge: The study coordinator will conduct a follow up phone call to all subjects four weeks after discharge summary is completed to obtain the level of physical activity using the IPAQ short form questionnaire. This is for research purposes only. A follow-up on a subject will be discontinued if a subject is not reached after three attempts of follow-up phone call made on three different days between 30 and 45 days. Data analysis will commence once all the data from 54 subjects are collected.

Table 1. Summary of Interventions for VRWP, VRW and VR Groups.

VRWP (n=18)	VRW (n=18)	VR (n=18)

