
 Visit 1: Test-retest of TUG. Subject will complete the IPAQ-short form. Randomization. Initiate or continue with VR. Visit 2: initiate HEP on walking with pedometer. Patients will be given a pedometer and instruction on how to use it. Participants will be encouraged to increase their daily steps at least 10% until they achieve at least 3,000 steps daily. Visit 3 to visit prior to discharge: Continue with VR. Continue with instruction on how to use the Fitbit Zip pedometer as needed. Treating therapist will monitor and keep a record of the 	
 Visit 1: Test-retest of TUG. Subject will complete the IPAQ-short form. Randomization. Initiate or continue with VR. Visit 2: Initiate HEP on time-based walking. Patients will be instructed to walk at least 10 minutes at a time. Participants will be encouraged to increase their daily steps at least 10% until they achieve at least 30 minutes of walking exercise daily. Visit 3 to visit prior to discharge: Continue with VR. Treating therapist will monitor and keep a record of the patient's daily step log form every visit. Discharge day: mCTSIB, DGI, 	
 Visit 1: Test-retest of TUG. Subject will complete the IPAQ-short form. Randomization. Initiate or Continue with VR. Visit 2 to Visit prior to discharge: Continue with VR, without the encouragement of walking and without specification of walking in the home exercise program. Discharge day: mCTSIB, DGI, DHI, TUG and IPAQ short form, total number of visits and length of intervention (in weeks). Four-week follow-up: phone call for IPAQ short form Pedometers will be mailed to participants as a reward for

patient's daily step log form every visit.
 
 • Discharge day: mCTSIB, DGI, DHI, TUG and IPAQ short form, total number of visits and length of intervention (in weeks) • Four-week follow-up: phone call for IPAQ short form 	
DHI, TUG and IPAQ short form, total number of visits and length of intervention (in weeks).
 
 • Four-week follow-up: phone call for IPAQ short form • Pedometers will be mailed to participants as a reward for participation. 	
participation.

---	--	-----------------------

Study Duration

TIMELINE

Month	Task	2017 Dec	2018 Jan	Feb	Mar	Apr	May	June
IRB Submission		X						
Protocol Set		X						
Completion of Training Requirements by Research Personnel		X						

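### Minor and optional: VR and VRW subjects are taught pedometer use at or before discharge, ahead of the four-week IPAQ; the teaching could move to after that call at little cost

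*Combined protocol and SAP*

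**What the plan says.** All references are to the Combined protocol and SAP.

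- **Teaching in VR and VRW (Study Procedures, Randomization).** These subjects get the device once they have completed the study. The next sentence covers the teaching: "They will receive instructions on how to use the pedometer prior or on the day of their last visit".
- **Teaching in VRWP (Randomization; Table 1, Visit 2).** Instruction is listed as part of this arm's package: "They will receive pedometers (Fitbit Zip), instructions on how to use the pedometer, step log forms". Table 1 starts device and teaching together: "Patients will be given a pedometer and instruction on how to use it".
- **The last visit (Study Visits).** "Discharge or last visit: All outcome measures (DGI, TUG, mCTSIB, DHI and IPAQ) will be reassessed".
- **The four-week outcome (Study Visits).** The coordinator is to "conduct a follow up phone call to all subjects four weeks after discharge summary is completed to obtain the level of physical activity". Follow-up of a subject stops if the subject is "not reached after three attempts of follow-up phone call made on three different days between 30 and 45 days".
- **IPAQ recall (Background).** "The short form records the amount of time spent in sitting, walking, moderate- and vigorous-intensity activities in the last 7 days".
- **Use of the outcome (Study Objectives, second purpose).** IPAQ change is assessed over the episode of care and "on four-weeks follow-up compared to those patients who only received instructions to walk without a pedometer".
- **Delivery of the device (Table 1, VRW and VR columns).** Mailing of the pedometer is the last item, after the four-week call. The columns do not mention pedometer teaching.

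**The concern.** Objective 2 asks what a pedometer adds to a walking instruction. The comparison is cleanest if nothing specific to the pedometer arm reaches the other arms until the last IPAQ has been recorded. The plan holds back the device but not the teaching, and the protocol itself counts the teaching among the things VRWP subjects receive. VR is also defined by the absence of encouragement to walk, and a lesson on a step counter sits a little awkwardly with that.

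At stake is the four-week IPAQ contrast between VRWP and VRW, and the three-group comparisons in which VR also appears. A lesson could prompt some subjects to walk more or to buy a device of their own. The comparison of log compliance does not use the IPAQ. The four primary outcomes (mCTSIB, TUG, DGI, DHI) are last measured at discharge.

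**Working it through.** The plan gives no figure on this point to reproduce, so the check is one of sequence, followed by simple counts.

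**Order of events for a VR or VRW subject**

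1. Admission IPAQ, at research Visit 1.
2. Pedometer teaching, on or before the last visit. No earliest date is given.
3. Discharge IPAQ, at the last visit.
4. Four-week IPAQ, by phone. A phone call is not a visit, so the last visit cannot mean this contact.
5. Device mailed, by the order of Table 1.

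Step 2 always precedes step 4, and it may precede step 3.

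**How many subjects.** VR 18 + VRW 18 = 36, and 36/54 = 67% of the planned sample.

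**Which recall days follow the teaching.** Let day 0 be discharge, and assume the discharge summary is completed on or after that day.

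- Four-week IPAQ: the call is at day 28, with the latest attempt at day 45. The 7-day recall starts at day 28 − 7 = 21, or at the latest day 45 − 7 = 38. The teaching is at day 0 or earlier, so 7 of 7 recall days follow it.
- Discharge IPAQ: if taught d days before discharge, min(d, 7) of 7 recall days follow. This gives 0 for d = 0, 3 for d = 3, and 7 for d ≥ 7.

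**Which comparisons use the four-week value.** Data Analysis, Objective 2, takes 2 scores (IPAQ-Walk, IPAQ-Total) over 3 periods (pretest to posttest, posttest to four weeks, pretest to four weeks): 2 × 3 = 6 comparisons. Two periods use the four-week value, so 2 × 2 = 4 of the 6.

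These counts describe exposure. None of them estimates a bias.

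**Direction.** Let D be true walking in VRWP minus walking in a comparison arm without the teaching, and let the teaching add δ ≥ 0 to the comparison arm. The observed difference is D − δ. If D > 0, a small δ (below 2D) brings it closer to zero. If D ≤ 0, any δ > 0 moves it further from zero. Attenuation therefore depends on VRWP walking more, which is what the trial sets out to learn.

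**What the comparison arms do not get.** Randomization reserves the device, the 3,000-step goal and the pedometer step log for VRWP. VRW has a time-based goal and a walking log. Table 1's VRW column speaks of steps and a step log. Without a device these subjects have no study step count, so I take this to mean the walking log.

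**The case against.** The strongest reply is that operating instructions without a device are hardly an intervention. What separates the arms is the device, the step goal and the step log, and all three are withheld. The protocol does not say that the walking goals or the walking handout accompany the lesson, so no rule about the VR arm is clearly broken. Discharge is the last face-to-face contact, and the subjects are aged 65 or older with dizziness, so teaching them in person then is a sensible practical choice. Most of this stands, and it is why the point is small. What remains is that the order is avoidable, and that by Table 1 the subjects are taught at least four weeks before they hold the device.

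A reader might draw stronger conclusions that the documents do not support:

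- **That the comparison arms get the pedometer before the four-week IPAQ.** Table 1 places mailing after the call, and the shipping budget in Resources Available fits mailing. The wording about completing the study is not tied expressly to the call, but that needs clarification only.
- **That teaching before the discharge IPAQ is planned.** The wording allows it, and nothing more.
- **That the bias is toward no difference.** This depends on the sign of D, as shown above.
- **That 36 of 54 subjects or 4 of 6 comparisons measure the harm.** They show who and what is exposed to an effect that may be nil.

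**Conclusion.** The sequence is clear from the text: in VR and VRW, pedometer instruction comes before the four-week IPAQ used for Objective 2. This is a minor, optional improvement and does not undermine the trial. The documents give nothing from which to size the effect of instruction without device, goal or log, and it is probably very small. The exposed result is the four-week IPAQ. The discharge IPAQ is exposed only if teaching is given earlier than the day of discharge.

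The conclusion assumes that the last visit is the discharge visit, that the discharge summary is not completed before it, and that the device is mailed in the order Table 1 gives. If a site took completion of the study to mean discharge and released the device then, the concern would be larger, but nothing suggests that this is intended.

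**What to change.** **If subjects are still to be taught.** Replace the sentence in Randomization with: VR and VRW subjects receive instructions on pedometer use only after the four-week IPAQ has been recorded, or after call attempts have ended without contact. Put a printed sheet in the mailed parcel, and have the coordinator explain the device briefly at the end of the call. Resources Available lists Fitbit Zip instruction for the research staff, not the coordinator, so add the coordinator to that training. As a clarification, tie completion of the study to the same point in Randomization and in Ethical Considerations.

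**Cost.** No new visit or call is needed, because the call and the shipping are already planned. The additions are one sheet per parcel, a few minutes per call and the coordinator's training. The downside is that these subjects lose hands-on teaching, and those not reached by phone have the sheet only. The loss concerns a post-study reward.

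**If subjects have already been taught.** Data Analysis is written in the past tense, so this may be the case. State as a limitation, beside the four-week IPAQ result, that VR and VRW subjects received instruction before that measurement. Give the timing by arm where visit records show it; the data templates listed under Data Confidentiality, Storage, and Retention do not name a teaching date. Do not assert the direction of any bias as fact.

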All statistical analyses were performed using SPSS version 26. Mean and standard deviation were used to describe interval and ratio data, and frequencies for nominal data. Statistical significance was set at alpha <0.05. Since the parameters of a normal distribution were not met, nonparametric statistical tests were chosen for statistical analysis.

Objective 1. To evaluate the impact of walking as an exercise component of VR on both primary and secondary vestibular-specific outcome measures.

Mean and standard deviations on the mean differences of pretest and posttest of TUG, DGI, DHI, and mCTSIB were calculated to compare walking (VRWP + VRW) and control groups (VR only). P-value was calculated using the Kruskal-Wallis test to check for between-group differences in the primary and secondary outcomes. For within-group differences, the Wilcoxon Signed Rank Test was used to examine significant differences between the pretest and posttest.

Objective 2. To evaluate whether pedometers increase the adherence of older adults with vestibular issues to a walking program.

To compare the VRWP, VRW and VR groups, IPAQ-Walk and IPAQ-Total scores were categorized as improve, same or decline in pretest and posttest, posttest and four-weeks follow-up, and pretest and four-weeks follow-up. P-value was calculated using the Kruskal-Wallis test to check for between-group differences of sociodemographic data, IPAQ-Walk, IPAQ-Total, compliance in meeting step goals and compliance in step log. Friedman's 2-way ANOVA by ranks test was used to examine significant differences within the group.

Objective 3. To establish test-retest reliability of the TUG test on older adults with dizziness.

Intraclass Correlation Coefficient (ICC) was calculated using the two-way mixed model, consistency type on a single measure model with a 95% CI for relative reliability. For absolute reliability, the Standard Error of Measurement (SEM), Minimal Detectable Change (MDC) 95% CI, and Bland-Altman 95% level of agreement were examined. The SEM provides the range of scores on retesting. A smaller value of SEM means the calculated score is close to the true score.⁴⁴ The MDC is used to reflect the true change in score that exceeded the errors of measurements. Both the SEM and MDC are the same units of the original measures, which allows easier interpretation of results when applied in the clinical practice.⁷⁴

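### The TUG test-retest data come from a single visit, so the MDC for Objective 3 leaves out day-to-day variation and is too small a threshold for change between visits

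*Combined protocol and SAP*

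**What the plan says.** Study Objectives gives the aim: "The third purpose of this study is to establish test-retest reliability of the TUG test on older adults with dizziness". Under Study Visits, Visit 1, the procedure is that "there will be one practice trial followed by two final performances that will be included in the data analysis". Table 1 places it at the same point in all three arms: "Visit 1: Test-retest of TUG. Subject will complete the IPAQ-short form". Neither place gives the interval between the two performances, and no later retest is scheduled for reliability.

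Data Analysis, Objective 3, names the statistics. For relative reliability, "Intraclass Correlation Coefficient (ICC) was calculated using the two-way mixed model, consistency type on a single measure model". For absolute reliability, "the Standard Error of Measurement (SEM), Minimal Detectable Change (MDC) 95% CI, and Bland-Altman 95% level of agreement were examined". It then explains the threshold: "The MDC is used to reflect the true change in score that exceeded the errors of measurements". It adds that SEM and MDC share the units of the measure, "which allows easier interpretation of results when applied in the clinical practice". Nothing limits this reading to repeat measurements within one session.

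A separate TUG exists. Study Visits lists TUG among the items for which "the following data will be collected as standard of care by the physical therapist during initial evaluation", or at the first follow-up appointment if time runs short. The study coordinator extracts it from the chart as the baseline value. The reliability analysis does not use it.

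**The concern.** Two performances at one visit share the patient's state on that day. Whatever is particular to the day cancels when one is subtracted from the other, so the spread of the differences shows trial-to-trial error alone. A clinician who reads an MDC as the threshold for true change will usually compare scores from different days. In this study TUG is measured at admission and discharge, and the length of intervention is recorded in weeks.

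The protocol's background makes zero day-to-day variation hard to assume. It names recurrent vestibulopathy and Meniere's disease among the peripheral conditions of older adults, and it describes activity limited by the expectation of a dizziness episode.

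The objective has its own planned paper. The protocol also says that no study has tested TUG test-retest reliability in older adults with dizziness, and that no MDC is established for them. A threshold that is too small would have no other figure beside it as a check, and ordinary fluctuation could be read as improvement.

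**Working it through.** **Inputs.** From the documents: one practice trial and two analysed trials, all at Visit 1; a 95% MDC. The documents state no TUG SD, SEM, ICC value or MDC value, so there is no figure to reproduce. The SDs below are assumptions chosen to show a range.

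**Model.** Score = person + day effect (variance var_day) + trial error (variance var_trial).

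- Two trials on one day: the day effect cancels, so SEM² = var_trial. Computing the SEM as SD × sqrt(1 − ICC) gives the same result. The same-visit ICC counts the day effect as agreement, and SD² × (1 − ICC) = var_trial.
- Two trials on different days: SEM² = var_trial + var_day.
- MDC = 1.96 × sqrt(2) × SEM = 2.772 × SEM.
- Ratio of between-day to same-visit MDC = sqrt(1 + var_day/var_trial). It is 1 only if var_day = 0.
- Share of unchanged patients whose between-day difference exceeds the same-visit MDC = 2 × [1 − Φ(1.96/ratio)].

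**Numbers (assumed SDs, in seconds).**

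| Trial SD | Day SD | Same-visit MDC | Between-day MDC | Ratio | Unchanged patients flagged |
|---|---|---|---|---|---|
| 0.6 | 0.3 | 1.66 | 1.86 | 1.12 | 8% |
| 0.6 | 0.6 | 1.66 | 2.35 | 1.41 | 17% |
| 0.6 | 1.0 | 1.66 | 3.23 | 1.94 | 31% |
| 1.0 | 0.3 | 2.77 | 2.89 | 1.04 | 6% |
| 1.0 | 0.6 | 2.77 | 3.23 | 1.17 | 9% |
| 1.0 | 1.0 | 2.77 | 3.92 | 1.41 | 17% |

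Example, row 3: between-day SEM = sqrt(0.36 + 1.00) = 1.166; MDC = 2.772 × 1.166 = 3.23; ratio = 1.166/0.6 = 1.94; 1.96/1.94 = 1.01, which gives 31%.

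**Would the chart TUG serve as the second occasion?** If treatment has begun between the two measurements, true change with SD s adds to the difference, and the estimate becomes 1.96 × sqrt(2 × (var_day + var_trial) + s²). With assumed day and trial SDs of 0.8 s each:

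- same-visit MDC = 2.772 × 0.8 = 2.22;
- correct between-day MDC = 1.96 × sqrt(2.56) = 3.14;
- chart-based estimate with s = 1: 1.96 × sqrt(3.56) = 3.70;
- chart-based estimate with s = 2: 1.96 × sqrt(6.56) = 5.02.

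The same-visit figure is 29% too small (2.22/3.14 = 0.71). With s = 2 the chart-based figure is 60% too large (5.02/3.14 = 1.60).

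**The case against.** The best defence is that testing within one visit is a legitimate choice. It holds the patient stable at a time when vestibular rehabilitation (VR) may be under way, whereas a retest days later would mix error with recovery. The design is stated openly. That stands as a reason for the design, but not for reading its MDC as a threshold between visits.

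The size cannot be drawn from the documents, and a range of 4% to 94% does not separate a trivial understatement from a serious one. That also stands. Only the direction is certain, given some day-to-day variation.

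Three stronger readings are tempting, and the documents do not support them.

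- *The trial's own TUG comparison is distorted.* Objective 1 compares pre-post differences with Kruskal-Wallis and Wilcoxon tests and applies no MDC responder rule. The harm lies in later use of a published threshold.
- *The trials are minutes apart.* That is likely, but the documents fix only the visit.
- *The chart already holds a clean retest, which would give an upper bound.* Consent may be returned at any time before the tenth visit, and at Visit 1 VR may be continuing. The chart value may come from the first follow-up. No practice trial, number of trials or same-rater rule is described for it. True change and procedural differences would probably inflate the estimate. In a small subset, though, sampling error alone could put it below the true value, so it is not a bound.

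**Conclusion.** The point holds as one of labelling and interpretation. The planned SEM, MDC and limits of agreement describe trial-to-trial repeatability within a session. For change between visits the MDC is too small by sqrt(1 + var_day/var_trial), unless day-to-day variance is zero. Over the assumed SDs the between-day MDC is 1.04 to 1.94 times the planned one, and the false-change rate is about 6% to 31% where 5% is intended. These figures rest on assumed SDs, approximately normal errors, and day effects independent of trial error. The conclusion limits what Objective 3 can claim and leaves the randomized comparison as it is.

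**What to change.** 1. In Study Objectives, Research Design, Visit 1, Table 1 and Data Analysis (Objective 3), call the result within-session, or trial-to-trial, reliability.
2. In Data Analysis, state that the SEM, MDC and limits of agreement exclude between-day variation, and that the MDC is a lower bound for change between visits. Do not offer it as a threshold for admission-to-discharge change.
3. Optionally, add an exploratory comparison of the chart TUG with the first analysed Visit 1 TUG, in subjects with a short gap and little or no VR in between. Report the number of subjects, the interval and the rater. Describe the result as approximate and probably inflated by true change and procedural differences, not as an upper bound.

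Items 1 and 2 cost only wording and a narrower claim for Objective 3. Item 3 needs some extra chart abstraction, because the visits and days before Visit 1 are not among the listed baseline variables. The eligible subset may be small; if it is too small to be useful, items 1 and 2 are enough.
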